7. INTERIM ANALYSES

7.1. Introduction

An interim analysis will be performed at least once annually while the study is ongoing, after at least 25% of participants are randomized, with further details provided in the IRC charter. This interim analysis will assess, at a minimum, unblinded safety of the randomized participants. Additional interim analyses for safety and/or efficacy may be performed if needed. Further details will be provided in the IRC charter.

Interim analysis results may be used for internal business decisions including, but not limited to: stopping a dose level, future study planning, stopping for futility, stopping for early success, conducting a sample size re-estimation, or adapting the study after the interim analysis. Before any interim analysis is instigated, the details of the objectives, decision criteria, information dissemination plan, and method of maintaining the study blind as per Pfizer's SOPs will be documented and approved in an IRC charter. In addition, the analysis details must be documented and approved in an interim analysis SAP or final SAP.

7.2. Interim Analyses and Summaries

The interim analyses will be performed using the methodology specified in this SAP and will be outlined in this SAP (with an amendment) or an interim analysis SAP. Any substantial deviations from the SAP's methodology will be fully justified and outlined. Details of the ongoing unblinded safety reviews will be provided in the IRC Charter and/or the interim analysis SAP.

PFIZER CONFIDENTIAL DMB02-GSOP-RF02 8.0 Statistical Analysis Plan Template TMF Doc ID: 98.03 Page 44 of 61

PFIZER CONFIDENTIAL DMB02-GSOP-RF02 8.0 *Statistical Analysis Plan Template* TMF Doc ID: 98.03 Page 45 of 61 15. HealthMeasures. http://www.healthmeasures.net/score-and-interpret/calculatescores/scoring-instructions. 2020.

PFIZER CONFIDENTIAL DMB02-GSOP-RF02 8.0 *Statistical Analysis Plan Template* TMF Doc ID: 98.03 Page 46 of 61

Analysis Plan
Statistical
(PF-06882961)
C3421019 (
Protocol

alyses
cacy An
of Effic
Summary
x 1. S
opendi
₹

Endpoint	Analysis Type	Population	Data Inclusion and Rules for Handling Intercurrent Events and Missing Data	Analysis Model
Percent change from	Summary	Estimand Set 1	DFI: Censor all values post discontinuation	A/A
baseline in body weight	Primary analysis		MV: Not imputed	MMMM
at End of Treatment	Supplementary analyses			Emax (x 2)
(and also at Weeks 2, 4. 6. 8. 10. 12. 16. 18	Exploratory analysis	Estimand Set 2	MPD: Remove participants	N/A
and 22 for Cohorts 1 &	Exploratory analysis		MV: Not imputed	MMRM
2 and at Weeks 4, 8, 12, 16, 20, 24 and 28 for Cohort 3)				
Response as defined	Summary	Estimand Set 1	DFI: Censor all values post discontinuation	N/A
of ≥5% from baseline	Summary		DFI: Censor all values post discontinuation	N/A
at End of Treatment	Secondary analysis		MV: Imputed using multiple imputation	Logistic
Absolute change from	Summary	Estimand Set 1	DFI: Censor all values post discontinuation	N/A
baseline in waist	Secondary analysis		MV: Not imputed	MMRM
circumference at End of Treatment (and at	`			
Weeks 2, 4, 6, 8, 10, 12 16 18 and 22 for				
Cohorts 1 & 2 and at				
Weeks 4, 8, 12, 16, 20,				
24 and 28 for Cohort				
3.)				
Absolute change from	Summary	Estimand Set 1	DFI: Censor all values post discontinuation	N/A
baseline in waist-to-hip ratio at End of	Secondary analysis		MV: Not imputed	MMRM
Treatment (and at				
Weeks 2, 4, 6, 8, 10,				
12, 16, 18 and 22 tor				
Cohorts 1 & 2 and at				

PFIZER CONFIDENTIAL DMB02-GSOP-RF02 8.0 *Statistical Analysis Plan Template* TMF Doc ID: 98.03 Page 47 of 61

Analysis Plan
Statistical A
PF-06882961)
C3421019 (
Protocol

	post discontinuation N/A	MMRM				post discontinuation N/A	MMRM							post discontinuation N/A	MMRM						ues (note this includes missing	
	DFI: Censor all values	MV: Not imputed				DFI: Censor all values	MV: Not imputed							DFI: Censor all values	MV: Not imputed	1					iations; MV = missing va)
	Estimand Set 1					Estimand Set 1								Estimand Set 1							major protocol devi	
	Summary	Secondary analysis				Summary	Secondary analysis	•						Summary	Exploratory analysis						ontinuation from IP; MPD =	censoring).
Weeks 4, 8, 12, 16, 20, 24 and 28 for Cohort 3.)	Absolute change from	baseline in HbA1c at Weeks 16 and 26 for	Cohorts 1 & 2 and at	Weeks 16, 24 and 32	for Cohort 3.	Absolute change from	baseline in FPG at	Weeks 2, 4, 6, 8, 10,	12, 16, 18, 22 and 26	for Cohorts 1 & 2 and	at Weeks 4, 8, 12, 16,	20, 24, 28 and 32 for	Cohort 3.	CFB in fasting plasma	insulin, HOMA-IR and	HOMA-B at Weeks 4,	8, 12, 16, 22 and 26 for	Cohort 1 & 2 and at	Weeks 4, 8, 12, 15, 20,	24 and 28 for Cohort 3.	Abbreviations: DFI = disco	values produced through c

End of Treatment is defined as Week 26 for Cohorts 1 and 2 and as Week 32 for Cohort 3.

PFIZER CONFIDENTIAL DMB02-GSOP-RF02 8.0 Statistical Analysis Plan Template TMF Doc ID: 98.03 Page 48 of 61

Appendix 2. Bayesian Statistical Methodology Details

Emax model without baseline interaction (Section 5.2.5)

A dataset (either .txt or .csv) of the following format should be produced by programming for use in R by the reporting statistician and QC statistician. Note, column headers should be labelled as specified below (including capitalization), as R is case sensitive:

Dose	Mean	SE
0	0	0.3
40	-0.01	0.4
80	-0.02	0.5
120	-0.03	0.3
160	-0.05	0.4
200	-0.1	0.5

Note the danuglipron dose groups refers to the results from the 1-week titration arms only, from the model described in Section 6.1.1.1. The Placebo group is the combined data from Cohorts 1 & 2. The residual standard deviation at End of Treatment from the unstructured covariance matrix from the associated MMRM will also be provided to the statisticians. The 4-parameter Emax model will be fit using the latest version (currently v2.1) of the clinDR package.¹¹ This analysis will be conducted by the study statistician. A different statistician will conduct QC of the analysis. The outputs of the analysis will be provided as .txt files to the programming team for inclusion in the final CSR table and figure formats.

Compound-specific information will be used to specify independent prior distributions for the placebo response (E_0), and the difference in response between the highest dose (*dTarget*=200 mg) and placebo, denoted by *difTarget*, based on data from the C3421002 study. Non-informative priors will be used for these parameters. Note that the E_{max} parameter is derived from the other parameters and is thus not explicitly supplied. The residual standard deviation, *sigma*, is assigned a uniform prior distribution over a range we are confident will include the population value.

Parameter	Prior
E_0	Normal(Mean = 0, SD = 6.8)
difTarget	Normal(Mean = -0.067, SD = 6.8)
sigma	Uniform(lb = 0.017, ub = 0.272)

In addition, the projected ED_{50} is $P_{50} = \sim 6$ mg based on data from the C3421002 study. It will be combined with the predictive prior distribution for the log(ED_{50}/P_{50}), obtained from metadata on approximately 225 compounds (from 3 references^{12,13,14}), to specify an informative prior distribution for the ED_{50} . The distribution of the Hill parameter is the predictive distribution from the meta-data. The current distributions are listed below. They are the default distributions in clinDR. These default distributions will be updated if the meta-data and their analysis are updated before the completion of the current study.

Parameter	Prior
log(Hill)	t (Mean = 0, SD = 0.84, df = 5)
log(ED ₅₀₎	$log(P_{50}) + t(Mean = 0, SD = 1.74, df = 5)$

PFIZER CONFIDENTIAL DMB02-GSOP-RF02 8.0 *Statistical Analysis Plan Template* TMF Doc ID: 98.03 Page 49 of 61 The bivariate predictive distribution of these parameters also includes a prior correlation, which is currently -0.43 based on the analysis of the meta-data, which also would be updated if the historical analysis is updated.

The default burn-in and number of samples will be utilized along with thinning of 20, which will include 3 chains to assess convergence. Model diagnostics will be examined including trace and auto-correlations plots. If these raise concerns over model convergence, additional burn-ins, samples and thinning will be attempted to improve convergence. Changes to the priors above may also be considered (e.g. increase precision of E_0 and *difTarget*) to improve convergence if deemed necessary. The final diagnostic plots will not be included in the clinical study report.

The following R code is included as an example that will be used as a basis for the analysis:

library(clinDR) compileStanModels() mmrmRes <- read.csv("LSmeans.csv",header=T,stringsAsFactors=F) # Determine 'effective' subject numbers based on MMRM SD at End of Treatment: mmrm_sd <- 0.068 # Provided by programming mmrmRes\$N <- trunc((mmrm_sd/mmrmRes\$StdErr)^2,0)

Set-up priors and MCMC options: prior_mmrm <- emaxPrior.control(epmu=0, epsca=6.8, difTargetmu=-0.067, difTargetsca=6.8, dTarget=200, effDF=9999, p50=6, sigmalow=0.017, sigmaup=0.272) mcmc_mmrm <- mcmc.control(chains=3,thin=20,seed=169)

Run Emax model: ### emaxMMRM <fitEmaxB(mmrmRes\$Estimate,mmrmRes\$dose,prior_mmrm,modType=4,count=mmrmRes\$N,msSat =mmrm_sd^2,mcmc=mcmc_mmrm)

Diagnostics and output: stan_trace(emaxMMRM\$estanfit) # Look at trace stan_dens(emaxMMRM\$estanfit) # Look at densities stan_ac(emaxMMRM\$estanfit) # Look at autocorrelation summary(emaxMMRM) # Summary of model parameters plot(emaxMMRM) # Look at fitted vs. observed data emaxMMRMout <- predict(emaxMMRM,dosevec=mmrmRes\$dose,clev=0.90) # Get dose predictions</pre>

Model parameters, posterior medians and 90%/95% credible intervals as specified in Section 5.2.5 will be output and provided back to the programming team after QC is complete.

Emax model with baseline interaction (Section 5.2.6)

A dataset of the same format to above should be produced by programming for use in R by the reporting statistician and QC statistician. Note, column headers should be labelled as specified (including capitalization), as R is case sensitive.

The residual standard deviations at End of Treatment from the unstructured covariance matrices from *each* of the associated MMRM models will also be provided to the statisticians.

PFIZER CONFIDENTIAL DMB02-GSOP-RF02 8.0 *Statistical Analysis Plan Template* TMF Doc ID: 98.03 Page 50 of 61 The same process for priors, model fitting, checking of model convergence and QC as above will be implemented for this model along with similar R code as to above. The only major difference in R code is the requirement to take the average of the residual standard deviations from the separate MMRM outputs which will be used as the global standard deviation in model fitting:

```
mmrmDoseRes <- read.csv(Dose_LSmeans.csv",header=T,stringsAsFactors=F)
# Covariance matrix:
mmrmDoseCov <- read.csv(Dose_CovParams.csv",header=T,stringsAsFactors=F)
# Calculate global SD:
mmrm_global_sd <- mean(mmrmDoseCov$SD)
# Merge datasets:
mmrmDoseRes <- merge(mmrmDoseRes,mmrmDoseCov,by="dose")
mmrmDoseRes <- merge(mmrmDoseRes,mmrmDoseCov,by="dose")
mmrmDoseRes$N1 <- trunc((mmrmDoseRes$SD/mmrmDoseRes$StdErr)^2,0)
mmrmDoseRes$N <- trunc((mmrmDoseRes$Glob_SD/mmrmDoseRes$StdErr)^2,0)
...
emaxMMRM Int <-</pre>
```

fitEmaxB(mmrmDoseRes\$Estimate,mmrmDoseRes\$dose,prior_mmrm,modType=4,count=mmrmDos eRes\$N,msSat=mmrm_global_sd^2,mcmc=mcmc_mmrm)

Model parameters, posterior medians and 90%/95% credible intervals as specified in Section 5.2.6 will be output and provided back to the programming team after QC is complete.

Appendix 3. Traditional Statistical Methodology Details

The following SAS code is to be used as a guide for implementation.

Example SAS code for MMRM Model (strata included):

Example SAS code for Cumulative Incidence Plots:

```
proc lifetest data = dataset method=km plots=cif(test) outcif=cifatrisk intervals=0 to 20 by 2;
strata treatment;
time day*censor(1)/eventcode=0;
```

run;

NOTE: the censor variable has a value = 1 when the related time is censored and has a value = 0 when the event of interest occurs. There should be no other values available for this censored variable in this dataset (including missing values). If required, missing observations should be removed prior to analysis.

PFIZER CONFIDENTIAL DMB02-GSOP-RF02 8.0 *Statistical Analysis Plan Template* TMF Doc ID: 98.03 Page 51 of 61

Example SAS code for Proportion of Responses (with multiple imputation):

Assume the SAS dataset is in a long format. The variable 'treatment' should be coded similar to 'Placebo', 'Danuglipron 40 mg BID', 'Danuglipron 80 mg BID',... 'Danuglipron 200 mg BID', 'Danuglipron 120 mg BID (2-week titration)', 'Danuglipron 160 mg BID (2-week titration)' and 'Danuglipron 200 mg BID (2-week titration)' so that when sorted in descending order 'Placebo' comes first.

proc sort data=analysis out= analysisl;

```
by subjid time treatment strata;
```

run;

```
* Create wide dataset for multiple imputation;
proc transpose data= analysisl out=analysisw prefix=week;
by subjid treatment strata;
id time;
var cfb_log;
```

run;

* Perform multiple imputation;

proc mi data=analysisw seed=169 nimpute=20 out= analysis_mi;

class treatment strata;

fcs nbiter=10 reg(/details);

var base treatment strata week2 week4 week6 week8 week10 week12 week16 week18 week22 week26;

run;

* Determine responders and non-responders at End of Treatment for all imputed datasets; data analysis mi 26;

```
set analysis_mi;
value = week26;
if value < log(0.95) and week26 ne . then resp = 1;
if value >= log(0.95) and week26 ne . then resp = 0;
```

run;

```
* Create datasets and combine proportions;
proc freq data=analysis_mi_26;
tables imputation *dose*resp/out=prop mi outpct;
```

run;

data prop_mi_0; set prop_mi; if resp=0; keep _imputation_ treatment count; rename count=count_0; run; data prop_mi_1; set prop_mi; if resp=1;

if resp=1; keep _imputation_ treatment count; rename count=count_1;

run;

```
data prop_mi_combined;
```

PFIZER CONFIDENTIAL DMB02-GSOP-RF02 8.0 *Statistical Analysis Plan Template* TMF Doc ID: 98.03 Page 52 of 61

```
merge prop_mi_0 prop_mi_1;
by _imputation_ treatment;
total = count_0 + count_1;
p = count_1/total;
q = count_0/total;
se_p = sqrt((p*q)/total);
```

run;

```
proc sort data=prop_mi_combined;
by treatment _imputation_;
proc mianalyze data=prop_mi_combined alpha=0.1;
by treatment;
modeleffects p;
stderr se_p;
ods output parameterestimates=prop_mi_out;
run;
```

Example SAS code for Logistic Regression Model (with multiple imputation):

The same imputed datasets as produced above for the 'Proportion of Responses' will be utilized. Note: the imputed dataset should be ordered so that the group 'Placebo' and 'Resp'=1 comes first to ensure that the reference group is Placebo and the odds ratios are for a response = 1.

```
* Fit logistic regressions to each imputed dataset and combine results;
proc sort data=analysis_mi_26;
        by _imputation_ descending treatment descending resp;
proc logistic data = analysis mi 26 order=data;
       by imputation ;
       class resp treatment strata;
       model resp = treatment strata base/alpha=0.1;
       oddsratio dose/diff=all:
       ods output OddsRatiosWald=OddsRatiosWald mi;
run;
data OddsRatiosWald mi;
       set OddsRatiosWald mi;
       if effect = . then delete;
       estimate = log(OddsRatioEst);
       SE = (log(UpperCL) - log(LowerCL))/(2*QUANTILE('NORMAL',0.95));
run:
proc sort data=OddsRatiosWald mi;
       by effect imputation ;
proc mianalyze data=OddsRatiosWald mi alpha=0.1;
```

```
by effect;
modeleffects estimate;
stderr SE;
ods output parameterestimates=OddsRatiosWald_mi_out;
```

run;

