6.3. Measures to Minimize Bias: Randomization and Blinding

6.3.1. Allocation to Study Intervention

[figure not shown]
Assignment of placebo in the run-in period and allocation of participants to treatment groups for the double-blind treatment period will proceed through the use of an IRT system (IWR). The site personnel (study coordinator or specified designee) will be required to enter or select information including but not limited to the user's ID and password, the protocol number, and the participant number. For the placebo run-in, the site personnel will then be provided with a DU or container number; for the double-blind treatment period, the site personnel will then be provided with a randomization number, and DU or container number(s). The IRT system will provide a confirmation report containing the participant number, randomization number, and DU or container number(s) assigned. The confirmation report must be stored in the site's files.

For Cohort 1, a randomization code using the method of random permuted blocks will be utilized to randomize eligible participants in 3:3:3:3:3:1:1:1 (placebo: 5 1-week titration PF-06882961 arms: 3 2-week titration PF-06882961 arms) prior to the first dose of double-blinded study intervention. For the additional participants enrolled as part of Cohort 2, a randomization code using the method of random permuted blocks will be utilized to randomize eligible participants in 1:2:2:2 (placebo: 3 2-week titration PF-06882961 arms) prior to the first dose of double-blinded study intervention. For Cohort 3, a randomization code using the method of random permuted blocks will be utilized to randomize eligible participants in 1:2:2:2 (placebo: 3 4-week titration PF-06882961 arms) prior to the first dose of double blinded study intervention. Participants will be randomized to 1 of the blinded study intervention regimens described in Table 3 for Cohorts 1 and 2, and Table 4 for Cohort 3.

Table 3. Target Doses for Randomized Regimens for Cohorts 1 and 2

| Regimen Description (dosed twice daily) | Cohort 1 | Cohort 2 | CCI | Total Number of Tablets per dose |
|---|----------|----------|-----|--|
| Placebo | х | Х | CCI | |
| PF-06882961 – 40 mg (1-week titration steps) | Х | | | |
| PF-06882961 – 80 mg (1-week titration steps) | X | | | |
| PF-06882961 – 120 mg (1-week titration steps) | X | | | |
| PF-06882961 – 160 mg (1-week titration steps) | X | | | |
| PF-06882961 – 200 mg (1-week titration steps) | X | | | |

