For Cohort 3, approximately 112 additional participants will be randomized (approximately 16 in the placebo and approximately 32 in each of the 3 PF-06882961 arms with 4-week titration steps). This sample size was selected to provide additional tolerability data using 4-week titration steps and provide acceptable operating characteristics for the primary endpoint. Assuming a discontinuation rate of 25%, it is expected that approximately 84 of these participants will complete the study, with approximately 12 completing the placebo arm and approximately 24 completing each of the PF-06882961 arms. For End of Treatment defined as Week 32, this yields 80% power to detect a placebo-adjusted reduction in body weight of (comparing PF-06882961 to placebo) at Week 32, using a 1-sided t-test at a 5% level and assuming a conservative SD on the loge-scale of for body weight change at Week 32, based on historical internal studies. If judged necessary by the sponsor to meet study objectives (for example, if the rate of discontinuation or rate of non-compliance is higher than anticipated), then up to approximately 140 participants may be randomized into Cohort 3, to ensure a sufficient number of completing participants.

Participants who withdraw from the study will not be replaced. Evaluable participants are defined as in Section 9.3.

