5.2.4. Logistic Regression

The logistic regression model(s) will include a term for treatment, strata (females versus males), and baseline will be included as a covariate.

Missing values (e.g. due to censoring) will be imputed for missing data using a multiple imputation method as described in Section 5.3.

The odds ratio for each treatment group of danuglipron relative to placebo and corresponding 90% confidence interval will be obtained.

Example SAS code is provided in Appendix 3.

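### Cohort 3 responder analysis: an imputed dataset with no placebo responders is lost from the pooled placebo rate and leaves all three odds ratios infinite, and the SAP has no fallback.

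*SAP*

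**What the plan says.** Protocol 9.4.3 fits the responder model to Cohort 3 separately from Cohorts 1 and 2. Protocol 9.2 plans "approximately 16 in the placebo and approximately 32 in each of the 3 PF-06882961 arms", so those placebo participants are the only reference group for three comparisons.

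SAP 5.3.1 creates 20 imputed datasets, obtains the response proportion by arm in each, and pools by Rubin's rules. SAP 5.2.4 fits a logistic model with treatment, sex and baseline, and states: "The odds ratio for each treatment group of danuglipron relative to placebo and corresponding 90% confidence interval will be obtained". The example code in SAP Appendix 3 does the following:

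- It tabulates responses with PROC FREQ to an output dataset, without the SPARSE option.
- It splits the output into responder and non-responder files, merges them, and computes "total = count_0 + count_1". The proportion and its standard error follow from that total.
- It fits PROC LOGISTIC by ordinary maximum likelihood, with placebo as reference, and recovers each standard error from the Wald limits for pooling.

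Appendix 3 calls the code a guide. Its example is for Week 26, and there is no Cohort 3 (Week 32) version.

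SAP 5.2.3 gives a fallback if the MMRM does not converge, and 5.2.5 and 5.2.6 give ordered fallbacks for the Emax models. Sections 5.2.4, 5.3.1 and 6.2.1 give none for an arm with no responders. The only flexibility there is to increase the number of imputations.

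**The concern.** A placebo arm of 16, with about 12 observed at Week 32, can plausibly contain nobody who lost 5%. Two steps then fail.

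**Pooled rate.** Without SPARSE, an empty cell produces no output row. The responder count is missing after the merge, and so are the total, the proportion and its standard error. A dataset whose placebo rate is truly 0 cannot contribute that 0. If the software skips it, only datasets with at least one responder are averaged, and the pooled placebo rate cannot fall below 1/16 = 6.25%. If the software stops, or all 20 datasets are empty, there is no estimate.

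**Odds ratio.** With no responder in the reference arm, the likelihood keeps rising as the placebo log odds go to minus infinity. Every active-versus-placebo contrast diverges, and adjusting for sex and baseline weight does not cure this.

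At stake are the Cohort 3 odds ratios for the first-listed secondary efficacy endpoint. Without a rule in the SAP, the remedy would be chosen after the problem had been seen in the data.

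**Working it through.** **Inputs from the documents.** Protocol 9.2 takes 25% discontinuation and 84 completers in total, split as follows: "with approximately 12 completing the placebo arm and approximately 24 completing each of the PF-06882961 arms". Check: 112 split 1:2:2:2 gives 16, 32, 32, 32; times 0.75 gives 12, 24, 24, 24, which sum to 84. The plan's figures reproduce. About 16 − 12 = 4 placebo values are therefore imputed. SAP Appendix 3 classes a log change below log(0.95) = −0.0513 as a response.

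**Assumptions.** The placebo response rate is not given and the planning SD is redacted. The one visible SD is the example value in SAP Appendix 2, "mmrm_sd <- 0.068 # Provided by programming". SDs of 0.05 and 0.04 are added to show the range. Mean placebo log change is taken as 0 (only the centre of a non-informative prior in Appendix 2) or as log(0.98) = −0.0202, a 2% loss.

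**Chance of an empty placebo cell.** Observed values are the same in every imputation. An empty dataset therefore needs all 12 observed participants to be non-responders, and with 20 imputations at least one empty dataset then almost always appears. So P(at least one) ≈ (1 − p)^12, where p = Φ((−0.0513 − mean)/SD).

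| Mean change | SD | p | (1 − p)^12 | Simulated |
|---|---|---|---|---|
| 0 | 0.068 | 22.5% | 4.7% | 5% |
| 0 | 0.05 | 15.2% | 13.7% | 14% |
| 0 | 0.04 | 10.0% | 28.3% | 28% |
| −2% | 0.068 | 32.4% | 0.9% | 1% |
| −2% | 0.05 | 26.7% | 2.4% | 2% |
| −2% | 0.04 | 21.9% | 5.2% | 5% |

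The simulation drew 12 observed values per trial and 20 proper normal imputations of the other 4.

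**Effect on the pooled rate.** In affected trials about 14 to 16 of the 20 datasets are empty. At mean 0 the pooled placebo rate is about 2% with the zeros kept and about 7.5% with them dropped. Averaged over all simulated trials at mean 0, dropping them adds about 0.3, 0.8 and 1.7 percentage points at SD 0.068, 0.05 and 0.04.

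**Effect on the odds ratio.** A Newton-Raphson logistic fit to one simulated Cohort 3 dataset (16/32/32/32, no placebo responder, sex and baseline included) gave, for the first active arm:

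| Iterations | Log odds ratio | SE |
|---|---|---|
| 5 | 4.45 | 5.5 |
| 12 | 11.45 | 182 |
| 20 | 19.45 | 9957 |

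The other two arms diverged in the same way. Rubin's total variance is T = Ū + (1 + 1/m)B, where Ū is the mean within-imputation variance and B the between-imputation variance. Nineteen ordinary datasets (mean log odds ratio 1.80, SE 0.85 each) pool to SE 0.88 and a 90% interval of 0.35 to 3.25. Adding one separated dataset, stopped at 10 iterations, gives SE 15.1 and −22.7 to 27.1. A Firth fit to the separated dataset gave finite log odds ratios of 1.82, 2.58 and 3.31, with SE about 1.5.

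**Other cohorts.** Combined Cohorts 1 and 2 expect about 50 placebo completers. Even at a 10% rate, 0.9^50 = 0.5%.

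The SAS code was read, not run. What SAS prints after separation, or does with a missing estimate, was not tested.

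**The case against.** **The code is only a guide.** True. SAP 5.3.1, followed literally, would give an empty dataset a proportion of 0. The block also needs rewriting anyway: it tabulates by a dose variable and then merges by treatment. The dropped-zero fault is therefore a correctable error in example code. The missing fallback for the odds ratio is not, because it is absent from the SAP text as well.

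**The error would be noticed.** A reader might infer that it is silent. The documents do not support that: SAP 6.2.1 also requires the response summary without imputation, and an empty imputed dataset implies zero observed placebo responders, which that summary would show. It would not repair the imputed rate or the odds ratios.

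**The probability rests on assumptions.** It does. Mean 0 is not a forecast, and Protocol 5.3.2 gives everyone counselling towards an energy deficit, so some placebo loss is plausible; at 2% the risk falls to about 1% to 5%. Protocol 9.2 also allows "up to approximately 140 participants may be randomized into Cohort 3". That is 20 placebo and 15 completers, and (1 − p)^15 at mean 0 gives about 2%, 8% and 21%. A smaller SD cannot be ruled out because the planning value is redacted.

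**The consequence is limited.** It is. SAP 5.1 confines formal testing to the primary endpoint.

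**Conclusion.** The point holds for Cohort 3. A dataset with no placebo responders makes the imputed placebo rate too high or unavailable under the example code. Under SAP 5.2.4 it leaves all three odds ratios without a finite estimate, and one such dataset is enough to make the pooled estimate and interval unusable. Raising the number of imputations does not help when the observed count is 0 of 12.

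The chance runs from about 1% to 28% over the range shown. It rests on 12 observed and 4 imputed placebo values, normal log changes, and an assumed placebo mean and SD.

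A reader might infer that the responder results are biased in general. The documents do not support that. The 7.5% against 2% contrast applies only to affected trials, and the average over all trials at mean 0 is 0.3 to 1.7 points. The dropped zeros raise the placebo rate, so they understate the response difference rather than favour the drug. The primary MMRM does not use these steps. This is worth correcting before unblinding, but it does not threaten the trial's main conclusion.

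**What to change.** 1. In the Appendix 3 code, use SPARSE in PROC FREQ, or set a missing responder or non-responder count to 0 before computing the total and proportion. A proportion of 0 or 1 then has standard error sqrt(pq/n) = 0, so specify a variance or interval that stays valid there, such as Wilson or an add-a-constant standard error. For example, adding 0.5 to each count for 0 of 16 gives 0.5/17 = 0.029 and a standard error of sqrt(0.029 × 0.971/17) = 0.041.
2. Add one sentence to SAP 5.2.4: if any arm in any imputed dataset has 0% or 100% responders, Firth penalised logistic regression will be fitted in all 20 imputed datasets for that cohort and those estimates pooled. The planned model stays in place when no such cell occurs.

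The cost is a few lines of code and one sentence. When the fallback is used, estimates shrink slightly towards no effect and intervals remain wide: with SE about 1.5, the 90% half-width is 1.645 × 1.5 = 2.5 on the log scale, a factor of about 12 either way.
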